Title: *Expanding the Diabetes Homelessness Medication Support (D-Homes) program to Spanish speaking Hispanics*

Short Title D-Homes Spanish Aim 2

Sponsor: National Institute of Diabetes and Digestive and Kidney Diseases
(R03DK133553-01)

IRB Number IRB-FY2023-556

NCT Identifier: NCT05819749

Protocol Date: August 21, 2023

Protocol Version: 4

Study Principal Investigator:

[name] [name], MSc
[name]
[name]
[contact]
email: [contact]

TABLE OF CONTENTS

Protocol Synopsis	iii
Table 1: Schedule of Study Procedures	vi
1 Background Information and Rationale	1
2 Study Objectives	4
3 Investigational plan	4
4 Study Procedures	7
5 Study Evaluations and Measurements	12
6 STATISTICAL CONSIDERATIONS	16
7 SAFETY MANAGEMENT	17
8 STUDY ADMINISTRATION	19
9 References	23

PROTOCOL SYNOPSIS

Study Title	Expanding the Diabetes Homelessness Medication Support (D-Homes) program to Spanish speaking Hispanics
Funder	National Institute of Diabetes and Digestive and Kidney Diseases (R03DK133553-01)
Clinical Phase	N/A
Study Rationale	People experiencing homelessness die on average 10 years earlier than their housed peers due to poorly controlled chronic physical and behavioral health conditions. The Hispanic community has disproportionately higher rates of both homelessness and diabetes. They have higher age-adjusted prevalence of diagnosed diabetes (1.6 times), earlier complications, and more diabetes-related death than non-Hispanic whites. Homelessness and unstable housing are common and increasing among Hispanic people. Access and insurance barriers compound individual challenges leading to even lower rates of medication adherence than general U.S. population.
Study Objective(s)	
Primary
 
 • To pilot test a behavioral intervention tailored to Spanish-speaking adults who have type 2 diabetes who have experienced homelessness or unstable housing using behavioral activation, motivational interviewing and psychosocial support to improve medication adherence (n=10-12) 
Secondary
 
 • To improve diabetes control (HgA1c)
Test Article(s)	Behavioral intervention to support medication adherence
Study Design	Single arm treatment-development trial
Subject Population	We will enroll adults (age \geq 18 yrs.) with type 2 diabetes who are experiencing homelessness.
Key Criteria for Inclusion and Exclusion:	
Inclusion criteria:
 
 1. Age 18 yrs. or older 2. Preferred language of Spanish 3. Experience of homelessness per the HEARTH Act (2011). 4. Self-reported diagnosis of type 2 diabetes, later verified in medical record and via A1c blood test 5. Plan to stay in local area or be reachable by phone for the next 16 weeks 6. Willingness to work on medication adherence and diabetes self-care

Exclusion criteria will include conditions raising risk for coercion or limitation of capacity to ethically consent to research:

1. Active intoxication (appears to be under the influence)
2. Active psychosis or dementia
3. Active legal commitment (per search of publicly available civil court records).
4. Pregnant or lactating at the start of the study.

This is aligned with previous studies by this team (K23DK118117, IRB # 19-4622).

Number Of Subjects	Total Number of Subjects: 10-12 Total Number at Hennepin Healthcare: Unknown Total Number of Sites: Assessments and coaching will primarily occur at Comunidades Latinas Unidas En Servicio (CLUES) service centers (see Letter of Support in Attachments) or at Hennepin Healthcare.
Study Duration	Each subject's participation will last 16 weeks. The entire study is expected to last one year.
Study Phases	(1) Screening : screening for eligibility and obtaining consent, baseline assessment
Screening	(2) Intervention : study intervention with counselor support approximately weekly in-person and/or by phone x 12 weeks
Intervention	(3) Follow-up : final assessment
Follow-Up	
Efficacy Evaluations	
• Self-reported medication adherence• Self-reported psychological wellness• Self-reported diabetes self-management, distress• Hemoglobin A1c measured by venipuncture at Hennepin Healthcare Lab or using at-home A1c test kit and reporting the results to research staff
Safety Evaluations	Capacity to consent for this at-risk patient population will be assessed using a quiz. Adverse events will be tracked as below.
Statistical And Analytic Plan	The primary endpoint of this study is the feasibility and acceptability of the program to participants in this treatment development phase. We will summarize themes in the end-of treatment interview, assess satisfaction via structured survey, and assess treatment dose received via frequency, length, and type of communications with study staff. We will conduct exploratory analyses on our eventual primary behavioral endpoint of medication adherence and compare this with change in our eventual primary clinical endpoint of point-of-care Hemoglobin A1c during this same time frame. We will refine our

use of patient-reported outcomes and administrative claims data for use in the future, planned randomized pilot trial.

Data And Safety Monitoring Plan

[name] (PI) will work closely with study staff to monitor the quality of data collected at assessment. This treatment development study (N=10-12), does not meet NIH criteria requiring a Data Safety Monitoring Board (DSMB), however [name] will oversee a detailed safety monitoring plan.

TABLE 1: SCHEDULE OF STUDY PROCEDURES

Study Phase	Eligibility screening	Consent, Baseline visit 1	Run-in, Baseline visit 2	Treatment sessions										Follow-up visit
Visit Number				1	2	3	4	5	6	7	8	9	10	
Study Weeks	0	1	2-3	2-3	4	5	6	7	8	9	10	11	12	13-16
Confirm communication preferences	X	X		X			X						X	
Review Inclusion/Exclusion Criteria	X	X	X											
Informed Consent		X												
Demographics/Medical History		X	X											
Medical records request/abstraction		X	X											X
Vital Signs: BP, HR		X	X											X
Height and Weight		X	X											X
Hemoglobin A1c		X	X											X
Medication review		X	X											X
Self-report survey measures		X	X											X
Satisfaction with intervention														X

1 BACKGROUND INFORMATION AND RATIONALE

1.1 Introduction

The overall goal of this project is to expand our team's existing evidence-informed programs to specifically target medication adherence to improve diabetes care among Spanish-speaking Hispanic adults experiencing homelessness or unstable housing in Minnesota and beyond. We plan a sequential exploratory mixed methods study design for treatment development familiar to our team from prior work (K23DK118117) with ongoing input from our community-engaged research team (Fig 2).

Aim 2. This protocol is part 2 of a set of studies with an overall goal to pilot test a collaborative care intervention using motivational interviewing and behavioral activation alongside education and psychosocial support to improve medication adherence tailored to the experiences of Spanish-speaking people experiencing homelessness and diabetes (DH-SH). Our team's central hypothesis is that medication adherence and diabetes self-care (and eventual glycemic control, health care use/cost) will improve with an intervention tailored to the unique context of DH-SH.

This work builds upon part 1 (IRB-FY2022-431) during which we completed Aim 1 activities to modify research and intervention tools from the Diabetes Homeless Medication Support (D-Homes) study to make them more culturally appropriate for Spanish-speaking patients. Data from this phase has identified barriers and strategies for medication adherence, patient values regarding medication, and treatment preferences and informed development of this part 2 application.

This protocol addresses Aim 2, to test patient perceptions of the feasibility and acceptability of study procedures and refine the D-Homes Spanish treatment manual through test cases (n=10-12) with a hypothesis that the D-Homes manual and study procedures will be feasible and acceptable to DH-SH as measured by self-report and post-treatment interview.

1.2 Significance

Homeless people in the US face disproportionate risk for premature death in part due to poorly controlled chronic diseases including diabetes. One and a half million unique US adults access homeless shelters annually.¹ People experiencing diabetes and homelessness develop complications 10 years earlier⁶ and die prematurely compared to their housed counterparts.⁸ Our region has

Box. Defining Homelessness:

Many definitions of homelessness exist. We adopt that of the U.S. government which includes people who:

- Lack "fixed, regular, adequate nighttime residence"
- Stay at emergency shelters, temporary living facilities, other places not meant for human habitation
- Will imminently lose their primary residence

(HEARTH Act, 2011)

accessible health insurance, health care, and prescriptions; however individual level barriers persist that are amenable to behavioral interventions.

Substantial evidence links medication adherence as a leading modifiable health behavior driving poor diabetes outcomes in low-income and homeless populations.^{11-13,15} Behavioral support for improved medication adherence among DH is the focus of our

team's **ongoing K23 award**. We've used qualitative data and multi-stakeholder input to develop a tailored behavioral intervention (the Diabetes Homeless Medication Support program [**D-Homes**]); pilot testing of this new intervention is ongoing. D-Homes offers 10 coaching sessions over 12 weeks targeting glycemic control via improved medication adherence. Coaching includes diabetes education and structured goal setting targeting medication adherence and psychological wellness.

[figure not shown]
Despite COVID-19-related challenges, we have successfully recruited 34 DH, 4 of whom identified as Hispanic. To date the existing K23 award (IRB # 20_4863) has required English fluency for enrollment due to limited resources.

The Hispanic community has disproportionately higher rates of both homelessness and diabetes. They have higher age-adjusted prevalence of diagnosed diabetes (1.6 times),²¹ earlier complications, and more diabetes-related death than non-Hispanic whites.^{22,23} Furthermore, Spanish-speaking Hispanic adults with diabetes demonstrate significantly lower medication adherence than their English-speaking Hispanic or non-Hispanic white counterparts.²⁵ Further, Hispanic people face "hidden homelessness" as they frequently share housing ("double up") and rely on informal shelter settings both of which are underestimated in homeless counts.^{29,30} Language barriers and widespread fear of utilizing public services like shelter due to undocumented status drive these differences.³¹ Moreover, emerging evidence suggests worsening of health care, medication, and housing access since the COVID-19 pandemic among Hispanics.³²

There is a *critical need* to include Spanish-speaking Hispanics in our ongoing D-Homes work to accurately reflect the demographics of DH nationally and locally. This R-03 application will extend the D-Homes work by adapting study materials for people experiencing Diabetes and Homelessness who are Spanish-speaking Hispanics (DH-SH) and collecting feasibility and acceptability data in this population. This will parallel the study procedures familiar to our team from our prior work with English-speaking DH (IRB # 20_4863).

1.3 Name and Description of Intervention

The behavioral intervention tested in this protocol is the Expanding the Diabetes Homelessness Medication Support (D-Homes) program to Spanish speaking Hispanics (DHomes-Spanish). This will be a 12-week in-person, video, and/or phone-based support program centered on providing diabetes education, motivational and goal-setting support, and resource and care coordination (Figure 2). Psychological approaches of behavioral activation and motivational interviewing will be used along with provision of educational materials and tools to support behavior change, see Section 3. for details.

1.4 Selection of Treatment Dosages

Treatment doses are similar to a multiple health behavior change intervention currently underway by [name] (“Development of an Integrated Depression and Behavioral Risk Factor Reduction Intervention for Secondary Prevention following Acute Coronary Syndrome,” 1R03HL136540), primary mentor on this study. This is also in line with current literature about behavioral interventions to support improved diabetes self-management via medication adherence and psychosocial wellness.⁹⁴ During this treatment development phase we will monitor and adjust the number and duration of planned sessions based on the data from case study participants. This will inform Aim 3 randomized pilot future steps.

1.5 Relevant References *See Section 10 for References.*

1.6 Compliance Statement

This study will be conducted in full accordance with all applicable Hennepin Healthcare Research Institute Policies and Procedures and all applicable federal and state laws and regulations including 45 CFR 46. All episodes of noncompliance will be documented.

The investigators will perform the study in accordance with this protocol, will obtain consent and assent, and will report unanticipated problems involving risks to subjects or others in accordance with Hennepin Healthcare Research Institute IRB Policies and Procedures and all federal requirements. Collection, recording, and reporting of data will be accurate and will ensure the privacy, health, and welfare of research subjects during and after the study.

All study materials have been translated into Spanish and back translated by credentialed, native Spanish speaking, staff members to verify accuracy of translation. All of these translations have been verified by participants in Aim 1 of this study. The consent form and HIPAA documentation were professionally translated.

2 STUDY OBJECTIVES

The purpose of the study overall is to improve the health of Spanish-speaking people with type 2 diabetes who are experiencing homelessness or unstable housing to complement the work of our team with English-speaking people. The purpose of the aim of the study is to develop and pilot test a collaborative care intervention using motivational interviewing and behavioral activation alongside education and psychosocial support to improve medication adherence tailored to the experiences of Spanish-speaking people experiencing homelessness and diabetes (DH-SH).

2.1 Primary Objective (or Aim)

The primary objective of this study is to determine whether a 10-session behavioral activation and motivational interviewing support program is feasible and acceptable to DH-SH. The outcomes we will use to assess this treatment development phase of our work will be our ability to recruit and retain participants, the dose of treatment we can deliver (i.e., participant's attendance and follow-up with scheduled sessions and treatment activities), and participants' report of their satisfaction and overall experience during participation in a structured survey and qualitative post-treatment interview.

2.2 Secondary Objectives (or Aim)

The secondary objectives will be to edit randomized pilot trial protocols and treatment manual instructions to optimally support participants. We will:

1. Clarify recruitment and retention strategies for DH-SH
2. Assess the acceptability of patient-reported outcome measures and laboratory testing protocols
3. Finalize plans to use administrative claims and health care record data
4. Determine adequate incentive amounts and adequate timing of distribution
5. Refine protocols for distribution of phones and other tools to support intervention participation and behavior change

3 INVESTIGATIONAL PLAN

3.1 General Schema of Study Design

This is a single arm pilot trial to inform development of the DHomes-Spanish behavioral treatment, see Table 1 above. The intervention, see Figure 1 above, targets diabetes education, motivation and goal-setting support, as well as resource and care coordination for Spanish-speaking people experiencing type 2 diabetes and homelessness (DH-SH). The goal of this treatment development phase of our work is to refine approaches and protocols for further study of our program.

3.1.1 Screening Phase and Baseline Assessment

Recruitment protocols are summarized in section 8.4 below but will involve (1) invitation to aim 1 research participants who indicated interest in future research, (2) referral from CLUES (3) phone calls to eligible patients at Hennepin Healthcare. Potential subjects will be screened by phone using the protocol inclusion and exclusion criteria.

Congruent with other trials in this area,⁴⁹ we will conduct a 2-week run-in period to ensure participants are able to follow-up. During this time two baseline assessment visits will be scheduled. The second baseline assessment visit will be scheduled to correspond to the first treatment visit whenever possible.

3.1.2 Study Intervention

This study will be offered to willing participants as an adjunctive to usual diabetes care. During the screening and run-in period, participants will be encouraged and supported to continue seeing their regular health care team. If they do not have one, support will be given to help the participant schedule a primary care or endocrinology appointment at Hennepin County Health Care for the Homeless, Hennepin Healthcare, or another clinic/health system per participant preference.

3.1.3 Follow-up and post-treatment interview

To be eligible for follow-up, subjects must either have completed their planned coaching sessions or requested to end their coaching sessions early. Since the emphasis of this treatment development study is feasibility and acceptability, those ending early will be given particular attention so that their insights and experiences can shape future adaptations to the intervention and study design. Follow-up will be done in the form of a post-treatment interview.

3.2 Allocation to Groups and Blinding *Not applicable to this phase of the study.*

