3.3 Study Duration, Enrollment and Number of Sites

3.3.1 Duration of Study Participation

Participants will be screened and recruited for a 2-week run-in period. They will engage in 10 weekly sessions over 12-weeks with our interventionist (“diabetes wellness coach”), and they will have a 4-week period within which to complete any missed visits and their final assessment visit, where they will complete assessment questions and the post-treatment interview. This is a maximum of 16 weeks duration per participant.

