4.3.6 Final Assessment

The final assessment visit will be completed within 4 weeks of completion of visit 10 or upon early termination. This will be completed by a research staff member who is distinct from the interventionist. The staff person will assess:

- Vital Signs: BP, HR
- Height and Weight
- Hemoglobin A1c
- Medication review
- Self-report survey measures
- Satisfaction with intervention

The staff person will also conduct the post-treatment interview.

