4.6 Subject Completion/Withdrawal

Subjects may withdraw from the study at any time without prejudice to their care. They may also be discontinued from the study at the discretion of the Investigator for lack of adherence to study treatment or visit schedules and AEs. If the Investigator becomes aware of any serious, related adverse events after the subject completes or withdraws from the study, they will be recorded in the source documents and on the case report form.

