4.6.1 Early Termination Study Visit

Any participant who withdraws will have no further study visits.

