Self-report survey measures	
Formal assessment surveys will be collected at Baseline Assessment 1 and/or Baseline Assessment 2 and 12-week assessment visits used as follows:
 
 1. Mental Health Inventory (MHI-5)¹¹⁵ 2. Health-related Quality of Life Short Form (SF-12)¹¹⁶ 3. Problem Areas in Diabetes (PAID)¹¹³ 4. Diabetes self-management questionnaire (DSMQ)¹⁰⁵ 5. Adherence to Refills and Medications Scales-Diabetes (ARMS-D)¹¹¹ 6. Self-reported medication adherence (Adherence Start with Knowledge, ASK-12)¹⁰⁶ 7. Basic needs survey¹⁰⁷ 8. Current and lifetime housing status 9. Use of substances 10. Brief Trauma Questionnaire¹⁰⁸ 11. Self-reported health care use
Satisfaction with intervention	
At the final assessment visit, the assessor (who is not the interventionist) will collect input about the participant's experiences during the intervention.
 
Participant satisfaction will be assessed by the Client Satisfaction Questionnaire, an 8-item measure developed in the mental health field,⁹⁵ and a qualitative post-treatment interview focused on experiences during participation from screening through final assessment visit. See interview guide.

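### Section 3.1.3 as written leaves satisfaction, a primary-endpoint component, uncollected for participants discontinued by the investigator or who stop attending without asking; 4.3.6 and 4.6.1 do not settle who gets the final visit.

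*Combined protocol and SAP*

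**What the plan says.** Four sections bear on who has a final visit.

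- 3.1.3 sets eligibility: "To be eligible for follow-up, subjects must either have completed their planned coaching sessions or requested to end their coaching sessions early". It adds that "those ending early will be given particular attention so that their insights and experiences can shape future adaptations to the intervention and study design".
- 4.3.6 sets timing: "The final assessment visit will be completed within 4 weeks of completion of visit 10 or upon early termination". It does not say whose decision the termination must be.
- 4.6 allows two exits from the study. One is the participant's: "Subjects may withdraw from the study at any time without prejudice to their care". The other is the investigator's: participants may "be discontinued from the study at the discretion of the Investigator for lack of adherence to study treatment or visit schedules and AEs".
- 4.6.1, headed as an early termination visit, says: "Any participant who withdraws will have no further study visits".

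Satisfaction is collected at one point only. Section 5.2 states: "At the final assessment visit, the assessor (who is not the interventionist) will collect input about" the participant's experience, using CSQ-8 and the post-treatment interview. Table 1 marks satisfaction in the follow-up column alone. Section 6.1 names satisfaction and overall experience, from CSQ-8 and that interview, as part of the primary endpoint. Section 6.3.2 summarizes CSQ-8 descriptively and gives no denominator for it.

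**The concern.** An acceptability measure is most informative when it includes people who did not stay with the program. The rule in 3.1.3 admits completers and those who asked to stop. It leaves out anyone the investigator discontinued, including for poor attendance, and anyone who drifted away without asking. These are plausibly the people for whom the program worked least well, and 3.1.3 itself wants to learn from those who end early. If the rule is followed literally, satisfaction is measured in a selected subset and may look more favorable than it would among everyone who began coaching. Because other sections can be read differently, two staff members could also treat the same participant differently.

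**Working it through.** **Step 1. Is follow-up in 3.1.3 the same visit as the final assessment in 4.3.6?** Yes. The synopsis describes the follow-up phase as the final assessment, Table 1 has a single follow-up column, and 3.3.1 places the interview at "their final assessment visit, where they will complete assessment questions and the post-treatment interview".

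**Step 2. Who is reached?** *Early termination* is undefined, so 4.3.6 is shown under a broad reading (any early end) and a narrow one (only the early ending described in 3.1.3).

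| Group | 3.1.3 | 4.3.6 broad | 4.3.6 narrow |
|---|---|---|---|
| Completed coaching | yes | yes | yes |
| Asked to stop coaching | yes | yes | yes |
| Discontinued by investigator | no | yes | no |
| Stopped attending without asking | no | yes, if this counts as termination | no |

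Under the broad reading the sections disagree about the last two groups. Under the narrow reading they agree, and both groups miss the visit. Neither reading closes the gap in 3.1.3. Section 4.6.1 sits under 4.6 and plausibly concerns only people leaving the whole study, but its heading reuses the term in 4.3.6.

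**Step 3. Are the data available elsewhere?** No.

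- The run-in (3.1.1) comes before coaching.
- The 4-week window (3.3.1) helps only those eligible for the visit.
- Session recordings and notes (8.1, 6.3.2) come from contact with the coach, whereas 4.3.6 requires satisfaction to be assessed by someone else.

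**Step 4. Size, for illustration.** The plan has no figure to reproduce: 6.4 gives n = 10-12 with no dropout rate, and no CSQ-8 SD appears.

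Inputs:
- N = number attending coaching visit 1; 10 and 12 are used, from 6.4.
- m = number unassessed under 3.1.3; assumed 0 to 3.
- d = how far below the assessed the unassessed would score, in SD units; assumed 0.5 to 1.0.

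Formulas:
- Coverage = (N − m)/N.
- Overstatement of the mean = (m/N) × d, because the mean of all N is the assessed mean minus (m/N) × d.
- Standard error of the assessed mean, in SD units = 1/√(N − m).

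Worked case, N = 12 and m = 2: coverage 10/12 = 83.3%; overstatement 2/12 × 0.5 = 0.083 to 2/12 × 1.0 = 0.167; standard error 1/√10 = 0.316.

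| N | m | Coverage | Overstatement, d = 0.5 | d = 1.0 | Standard error |
|---|---|---|---|---|---|
| 12 | 0 | 100% | 0 | 0 | 0.289 |
| 12 | 1 | 91.7% | 0.042 | 0.083 | 0.302 |
| 12 | 2 | 83.3% | 0.083 | 0.167 | 0.316 |
| 12 | 3 | 75.0% | 0.125 | 0.250 | 0.333 |
| 10 | 2 | 80.0% | 0.100 | 0.200 | 0.354 |
| 10 | 3 | 70.0% | 0.150 | 0.300 | 0.378 |

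If d = 0 the overstatement is 0 in every row. A bound that needs no assumption about d: if 8 of 10 are assessed and all 8 are satisfied, the reported 100% is compatible with 8/10 = 80% to 10/10 = 100% of those who began.

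**Step 5. What could better wording recover?** If r of the m are reached, the remaining overstatement is d × (N − m)(m − r)/[N(N − m + r)]. With N = 12 and r = 1:
- m = 2: 10 × 1/(12 × 11) = 0.076, so 0.038 to 0.076 SD; coverage 11/12 = 91.7%.
- m = 3: 9 × 2/(12 × 10) = 0.150, so 0.075 to 0.150 SD; coverage 10/12 = 83.3%.

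**The case against.** The strongest reply is that there is no contradiction. Section 3.1.3 says who is eligible and 4.3.6 says when the visit happens, so *early termination* may simply mean the early ending that 3.1.3 describes. Section 4.6 speaks of discontinuation from the study, not only from coaching, so a further visit may not have been intended. No termination event is defined for someone who silently stops coming, so 4.3.6 may not reach that person either. All of this stands. A reader might infer that the sections flatly contradict each other; with the terms undefined, the documents support only ambiguity. It does not rescue 3.1.3, whose own wording omits both groups on either reading.

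Second, the plan's intent is visible: it promises attention to those ending early, lets the number of sessions be adjusted (1.4), and collects backup contacts (4.3). That shows the means and the wish to reach these participants, which makes the narrow eligibility sentence an odd fit, but it does not override that sentence.

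Third, retention and attendance belong to the same endpoint and withdrawal is a secondary endpoint (6.2), so attrition will be reported beside CSQ-8. Session notes are also a listed source in 6.3.2. Both points limit the harm. Neither supplies CSQ-8 or an independent interview from those who left.

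Fourth, the sizes are assumed throughout, every shift is below one standard error, and CSQ-8 faces no threshold or test. That is correct. It limits the importance of the point, and it also means the data could not reveal such a shift.

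**Conclusion.** The point holds as a gap in 3.1.3 combined with ambiguity across 3.1.3, 4.3.6, 4.6 and 4.6.1. Followed as written, 3.1.3 leaves CSQ-8 and the exit interview missing for participants discontinued by the investigator and for those who stop attending without asking. It should be fixed because the primary endpoint is touched and the remedy is cheap, but the likely effect is modest.

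The gap rests on the text; its size does not. The illustrated 0.08 to 0.25 SD (2 to 3 of 12 unassessed) depends on assumed numbers unassessed and an assumed satisfaction gap. It is 0 if nobody falls in the two groups or if those unassessed are equally satisfied.

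Two stronger readings are not supported. A reader might infer that reported satisfaction will be biased upward; the documents give no dropout rate and nothing on how leavers would score, so bias is possible but not shown. A reader might also infer that the whole primary endpoint is compromised; recruitment, retention, dose and communication counts do not depend on this visit.

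**What to change.** 1. Reconcile 3.1.3, 4.3.6, 4.6 and 4.6.1 by defining three separate events: stopping coaching (by request or by no longer attending), discontinuation by the investigator, and withdrawal of consent for further contact. The documents are silent on contact after discontinuation, so the reconciled text has to state it. The change concerns data collection only, not when coaching should end.
2. Offer CSQ-8 and the exit interview to everyone who stopped coaching for any reason and has not withdrawn consent for contact, by phone where possible, using the contacts already gathered under 4.3.
3. In 6.3.2, report CSQ-8 and interview completion out of all who attended coaching visit 1, with the reason for each missing one. This denominator leaves out people excluded after consent but before coaching because diabetes was not confirmed.

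The cost is amendment wording in these sections and a few more invitations to a visit already budgeted at $60 per participant (8.6.2). Some non-attenders will remain unreachable under any rule; the change reduces that loss and makes the remainder visible.
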